#### 11 Procedures and assessments

A study flow diagram and schedule of procedures to be performed during the study is found in section 6 and Appendix 1. The intent of this large, pragmatic trial is to use routine clinical information whenever possible as an efficient strategy for protocol implementation and endpoint ascertainment.

#### 11.1 Recruitment

Participants will be recruited via one of three complementary routes: (i) the NHS Health Checks programme; (ii) individuals participating in existing research databases held by GLINT investigators; and (iii) search of GP electronic records using risk scores to identify potentially eligible individuals.

Potential participants will be sent information about the study. They will be invited to attend a local clinical research facility or to return to their participating study practice to discuss the study and undergo eligibility assessments performed by a suitably trained and qualified member of the research team or NIHR clinical research network nurses.

# 11.2 Baseline visit (Visit 1)

Suitably qualified and delegated members of the study team will undertake the process of seeking informed consent from individuals who are eligible to take part in the study.

Baseline visits will last approximately one hour following standard operating procedures undertaken by trained staff. A unique participant ID number will be allocated to all individuals considered for enrolment. The following data will be collected:

#### 1.Written informed consent

- 2.Socio-demographic data: age, gender, ethnicity
- 3. Medical history (including diabetes, CVD, cancer)
- 4.Biochemistry: Outstanding blood values (if not available in past 12 months), total cholesterol, LDL and HDL cholesterol, triglycerides, HbA1c, creatinine (if not available in past 6 months)
- 5.Blood pressure (3 measures to be recorded)
- 6.Modelled ten-year cardiovascular risk (QRISK2 / Framingham)
- 7.Clinical variables: height, weight

- 8.Questionnaire including self-reported morbidity (CVD, cancer, T2DM), health service use in the past 12 months, and health utility (EuroQol EQ5D).
- 9.In addition, with consent, we will centrally store a sample of whole blood for DNA analysis, and a serum and plasma sample for biomarker analysis.

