#### 6 Study Flow Chart

ANNUAL FOLLOW-UP UNTIL END OF STUDY All participants will be sent an annual questionnaire including questions on CVD, cancer and diabetes incidence; adverse events; medication adherence; SF8, EuroQol (EQ5D), treatment satisfaction; health service use in last 12 months; GPs will receive an annual questionnaire regarding vital status; CVD, cancer and diabetes incidence; adverse events; current medication; most recent eGFR value (if present)**	
---	--

\*Note that we do not plan to collect LFTs or B12 at baseline in the full study (following safety results from the feasibility phase); we do not plan to collect creatinine measures during study follow-up, (following safety results from the feasibility phase), although we will ask GPs to supply this value if available \*\* If eGFR < 45ml/min, study medication should be stopped

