#### 8.3 Number of Participants

A total of 12,898 eligible individuals will be recruited, 250 in the initial feasibility phase, and a further 12,648 over approximately a two year period. Participants will be randomly allocated to treatment with either metformin prolonged-release tablets or placebo, and followed up for a median of approximately five years. The sample size calculation for the study can be found in section 15.3.

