## 8.6.2 Secondary endpoint

- Time from randomisation to the first confirmed event of the individual components of the primary composite endpoint *i.e.* CV mortality, nonfatal myocardial infarction or nonfatal stroke.
- Time to any cause of death (supplied by Office of National Statistics)
- Time to first non-melanoma cancer diagnosis (supplied by National Cancer Registry)
- Time to death due to a non-melanoma cancer cause according to primary / underlying cause of death on death certificate (supplied by the Office of National Statistics)
- Physician diagnosed T2DM
- Participant satisfaction with treatment (adapted DTSQ) annually from randomisation and additionally at four months post-randomisation in the feasibility phase.
- Functional status (SF-8) annually from randomisation and additionally at four months post-randomisation in the feasibility phase.
- Health utility (EuroQol EQ-5D) annually from randomisation and additionally at four months post-randomisation in the feasibility phase.

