# GP/participant questionnaire Mail Out (Issued after 4 months, annually and at end of study)

Participant questionnaire

- Self reported morbidity (CVD, cancer, T2DM)
- Medication adherence
- Health service use in past 12 months
- EuroQoL EQ-5D
- Treatment satisfaction/SF-8
- Self-Adverse events

GP questionnaire

- Vital status i.e. alive or dead
- Morbidity (CVD, cancer, T2DM)
- Current prescribed medication
- Adverse events
- Whether participant has become pregnant

Participants and GPs will be instructed to return the completed questionnaires to the DTU in freepost envelopes. If necessary, reminders will be sent after 4 and 8 weeks for the annual questionnaire. Participants will be contacted by phone if they do not respond to the reminders. Annual questionnaires will not be sent within 4 weeks of the end of study questionnaires being issued.

Participants and GPs will be reminded about the potential risks of taking metformin when they receive their four month questionnaire in the feasibility phase and the annual questionnaire in the full study.

When a participant or GP indicates that a primary or secondary endpoint has occurred following receipt of the annual questionnaire, information on this event will be collected immediately. We will also use information from the Office for National Statistics, the Cancer Registry and Health Episode Statistics to assess whether participants have experienced a study endpoint.

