#### 11.3.2 Additional Information

•B12 levels, LFTs, total cholesterol, LDL and HDL cholesterol will be collected at baseline and 6 months. B12 and LFT results will be reviewed following the feasibility phase to inform a decision on whether it is necessary to include these measures in the full study.

•HbA1c and serum creatinine will be collected at baseline, 3 months, and 6 months. Baseline HbA1c and serum creatinine should be used for assessment of eligibility. Creatinine results will be reviewed following the feasibility phase to inform a decision whether it is necessary to centrally monitor renal function in the full study.

•Feedback about study participation, including how to optimise medication adherence, will be sought through the invitation of a subset of volunteers to participate in focus groups.

•We will use information received from the Office for National Statistics, the National Cancer Registry and Health Episode Statistics to assess clinical primary and secondary outcomes. Any events found will be added manually to the GLINT Trial Management System Database.

All participants in the feasibility phase of the study will continue into the full study and receive scheduled assessments as described in Appendix 1.

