# 24 Appendices

## 24.1 Appendix 1 Schedule of procedures

	Recruitment	Visit 1			Visit 2		Visit 3		
		Baseline	4	8	3	4	6	Annual GP /	End of
		(day 0) [2]	wks	wks	month	month	month	participant	study /
					visit*	mail-	visit*	questionnaire	early
						out*		[6]	termination
Demographic information (DOB, sex,	Х	Х							
ethnicity)									
Medical history information (including diabetes, CVD, cancer)	Х	Х							
Biochemistry: HbA 1c , TC, LDL, HDL,		X (if value n/a in past			Х		Х		
triglycerides		12 months)							
Biochemistry: Creatinine		X (if value n/a in past			Х		Х		
		6 months)							
Blood pressure		Х							
Modelled ten-year cardiovascular risk		X (if value n/a in past							
(QRISK2/Framingham)		12 months)							
Anthropometry: height, weight		Х							
Informed consent and stored blood sample		Х							
authorisation									
Randomisation		X [3]							
If consent obtained, a whole blood sample		Х							
will be taken for storage for future DNA									
analysis, and a serum and plasma sample									
for biomarker analyses									
Letter / lifestyle booklet / emergency card		Х							
sent to participant if inclusion criteria met;									
letter sent to GP informing them individual									
is in study									
Drug dispensation		X [4,5]							
Phone call to check titration competency and			Х	Х					
adverse events									
Feasibility phase									
HbA 1c , creatinine		X [7]			Х		Х		
B12 levels, LFTs, total cholesterol, LDL and		X [7]					Х		
HDL cholesterol									

GLINT Protocol

Version Date: 18/03/2016

	Recruitment	Visit 1 Baseline (day 0) [2]	4 wks	8 wks	Visit 2 3 month visit*	4 month mail- out*	Visit 3 6 month visit*	Annual GP / participant questionnaire [6]	End of study / early termination
Medication count					Х		Х		
Questionnaire sent to participant / GP						Х			
Participant questionnaire									
Self-reported morbidity (CVD, cancer, T2DM)		Х				Х		Х	Х
Medication adherence						Х		Х	Х
Health service use in past 12 months (adapted from HERC questionnaire)		Х				Х		Х	Х
EuroQol EQ-5D		Х				Х		Х	Х
Treatment satisfaction / SF-8						Х		Х	Х
Adverse events / side-effects					Х	Х	Х	Х	Х
GP questionnaire									
Vital status						Х		Х	Х
Morbidity (CVD, cancer, T2DM)						Х		Х	Х
Current prescribed medication						Х		Х	Х
Adverse events						Х		Х	Х
Whether participant has become pregnant						Х		Х	Х
Endpoint ascertainment									
ONS/national registry tagging for ICD-10 coded mortality		Х							

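### SF-8 functional status is a secondary endpoint but is not collected before randomisation, which gives up change from baseline, baseline adjustment and some precision

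*Protocol*

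**What the plan says.** Sections 8.5.2 and 8.6.2 list functional status by SF-8 as a secondary objective and a secondary endpoint. Its timing is "Functional status (SF-8) annually from randomisation and additionally at four months post-randomisation in the feasibility phase".

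The data collection sections are consistent with each other:

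- **Section 11.2, item 8** gives the baseline questionnaire as "Questionnaire including self-reported morbidity (CVD, cancer, T2DM), health service use in the past 12 months, and health utility (EuroQol EQ5D"). SF-8 is not named.
- **Section 11.3.2** gives the extra baseline measures of the feasibility phase. They are laboratory tests: "B12 levels, LFTs, total cholesterol, LDL and HDL cholesterol will be collected at baseline and 6 months", plus HbA1c and creatinine.
- **Section 11.3.1** puts "Treatment satisfaction/SF-8" on the mailed participant questionnaire, which is "Issued after 4 months, annually and at end of study".
- **Section 6 (flow chart)** places SF-8 in the annual follow-up: "medication adherence; SF8, EuroQol (EQ5D), treatment satisfaction; health service use in last 12 months".
- **Appendix 1** marks EQ-5D at baseline, the 4-month mail-out, the annual questionnaire and end of study. The next row, "Treatment satisfaction / SF-8", has the three later marks and no baseline mark.

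Section 10.4 adds that after the feasibility phase there are no research visits beyond baseline and follow-up is by post.

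**The concern.** SF-8 appears to have been scheduled together with treatment satisfaction, with which it shares a row. Satisfaction with a treatment cannot be asked before treatment starts; a general functional status form can. EQ-5D, a comparable self-completed form, is on the baseline questionnaire. The protocol gives no reason for treating the two differently.

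Three things are at stake for this endpoint. Change in functional status cannot be reported. The comparison between arms cannot be adjusted for its most direct baseline covariate. And participants who return later forms cannot be compared with those who do not on the outcome itself. The last matters because section 9.6.1 links the two: refusing the questionnaire is a stated reason for stopping study medication, and persistent failure to return it, followed by failed calls, stops the drug supply. Return of forms may therefore not be independent of experience on treatment.

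This is a gap in data collection, so an analysis plan could not repair it.

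**Working it through.** **Step 1: is there an SF-8 before randomisation anywhere?** Appendix 1, row by row:

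| Row | Baseline | 4-month mail-out | Annual | End of study |
|---|---|---|---|---|
| EQ-5D | yes | yes | yes | yes |
| Treatment satisfaction / SF-8 | no | yes | yes | yes |

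Sections 11.2 and 11.3.2 agree with this. The baseline part of the flow chart is not shown, so it could not be checked.

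**Step 2: when is the first SF-8?** Section 8.6.2 and Appendix 1 confine the 4-month form to the feasibility phase. Section 8.3 says "A total of 12,898 eligible individuals will be recruited, 250 in the initial feasibility phase", which leaves 12,898 − 250 = 12,648 whose first SF-8 is the annual form at about 12 months. Sections 9.6.1, 11.3.1 and 12.5 mention a 4-month questionnaire without that restriction. Even if it went to everyone, the first SF-8 would still follow randomisation.

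**Step 3: what would a baseline value buy?** The protocol gives no figure for SF-8 to reproduce. For a comparison of mean scores, adjusting for a baseline with correlation r to follow-up multiplies the variance of the difference by 1 − r², and the confidence interval width by √(1 − r²). The value of r is not in the documents; 0.3 to 0.7 is assumed.

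For scale, take the 16% loss in section 15.3 as a rough allowance for missing forms: 12,898 / 2 × 0.84 ≈ 5,417 per arm. In SD units the unadjusted standard error is √(2 / 5,417) = 0.0192, and the 95% half-width is 1.96 × 0.0192 ≈ 0.038.

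| r | Variance factor 1 − r² | Variance cut | Interval narrower by | Half-width (SD) |
|---|---|---|---|---|
| none | 1 | – | – | 0.038 |
| 0.3 | 0.91 | 9% | 5% | 0.036 |
| 0.5 | 0.75 | 25% | 13% | 0.033 |
| 0.7 | 0.51 | 49% | 29% | 0.027 |

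The largest absolute gain is 0.038 − 0.027 = 0.011 SD. The 16% allowance hardly matters: with all 6,449 per arm the half-width is 1.96 × √(2 / 6,449) ≈ 0.035 SD, or 0.035 × √0.51 ≈ 0.025 SD at r = 0.7.

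**Step 4: compared with what?** These reductions are against no adjustment at all. Baseline EQ-5D, morbidity, health service use and age are already collected. To the extent that they predict follow-up SF-8, the further gain from a baseline SF-8 is smaller. It cannot be sized, because the documents do not give the relevant correlations.

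**The case against.** The best defence is that nothing in the protocol is contradicted. The endpoint is defined as follow-up SF-8, no section promises change from baseline, and randomised arms can be compared on follow-up scores without a baseline. EQ-5D, the health utility measure and the natural input to the quality-adjusted life years in section 15.8, does have its baseline. In a large pragmatic trial, leaving a second health status form off the baseline visit is defensible. Section 15.1 plans no p-values for secondary endpoints, and with more than 5,000 per arm precision is not scarce. All of this stands, and it limits the point to an improvement.

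Two textual defences are weaker. The baseline questionnaire list is worded as non-exhaustive, and annual collection from randomisation could be stretched to include time zero. But section 8.6.2 uses the same timing words for treatment satisfaction, SF-8 and EQ-5D, and only EQ-5D has a baseline mark in Appendix 1. If a baseline SF-8 was intended, section 11.2 and Appendix 1 still need correcting.

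A reader might also infer more than the documents support:

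- *That the endpoint is biased or cannot be analysed.* With complete data the comparison between arms is unbiased. Covariates other than SF-8 remain available for adjustment and for describing non-returners.
- *That a baseline SF-8 would cure selection by response and survival at 12 months.* It would not. That selection affects every annual form, including EQ-5D. A baseline value only helps to describe it and to support a missing-data analysis. The protocol already sends questionnaires to those who stop medication (Appendix 1, note 5), with reminders and telephone contact (section 11.3.1).
- *That the 16% loss in section 15.3 counts participants left without any SF-8.* It is a loss assumption for the event-driven sample size, with median follow-up of about five years. It is not first-year questionnaire loss. People with no follow-up form would have no SF-8 outcome even if a baseline existed.

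**Conclusion.** The gap is real. SF-8 is a secondary endpoint with no scheduled measurement before randomisation, and for 12,648 of 12,898 participants the first value comes by post at about 12 months. Change from baseline, adjustment for baseline SF-8, and a comparison of returners with non-returners on SF-8 itself are not possible. Baseline EQ-5D and the other covariates are partial proxies.

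The consequence is modest. If r lies between 0.3 and 0.7, and mean scores are compared, the forgone variance reduction is 9% to 49% relative to no adjustment and smaller relative to adjustment for EQ-5D. In absolute terms it is at most about 0.011 SD on the 95% half-width in the full study. The validity of the randomised comparison is not in question. This is a cheap improvement worth making before full-study recruitment, since the value cannot be recovered for anyone randomised without it.

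**What to change.** 1. In section 11.2, add SF-8 to item 8 of the baseline questionnaire.
2. In Appendix 1, split the shared row. Mark SF-8 at baseline, annually and at end of study, plus the 4-month mail-out in the feasibility phase. Mark treatment satisfaction after baseline only.
3. State that the SF-8 comparison will be adjusted for its baseline value among participants who have one.

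The cost is eight more items on a questionnaire already completed at a visit of about one hour, and an amendment to the protocol and eCRF. Up to 250 feasibility participants already enrolled would have no baseline value. They can be handled with the existing covariates or left out of the adjusted analysis, with that choice stated in advance.

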## NOTE:

During the feasibility phase, additional baseline assessments are collected as described in Section 11.3.2. Baseline biochemical values should be used to assess eligibility during the feasibility phase. If baseline laboratory values reduce the CVD risk calculation to <20% and/or the HbA1c <36.6mmol/mol, the participant remains eligible based on the prior risk calculation. However, if eGFR is <45ml/min or HbA1c is  $\geq$ 47.5mmol/mol, the participant is ineligible.

If consent is given but the participant is not eligible to take part in GLINT (following receipt of biochemistry results from the baseline visit), research samples of whole blood and serum will be destroyed. Participants will be informed that they are not eligible for GLINT. Their GP will receive the clinical results and will be informed that their patient consented to take part in the study but was not eligible following the baseline visit. Travel expenses will be reimbursed according to local site policy.

Participants meeting the eligibility criteria will be randomised *i.e.* assigned to the next in sequence Randomisation Number. For participants requiring outstanding blood test values, randomisation will be delayed until all information necessary to assess eligibility is available. A duration of approximately fourteen working days will be allowed between attendance at a baseline visit and when participants are notified whether they have been included in the study or not (following assessment of outstanding blood tests). They will be randomised to metformin or placebo which they will receive by post direct from the IMP packagers in 16-weekly batches.

Participants who have been randomised will receive a best practice leaflet describing the benefits of lifestyle changes for CVD risk reduction and their GP will be sent a letter informing them that the participant has been enrolled in the GLINT. This letter sent to the GP will include the results of the baseline CVD risk assessment, information about the safety and tolerability of metformin, and what to do should the participant develop T2DM.

# 11.3 Study assessments

#### 11.3.1 Approximate timing of assessments

#### Week 4: Phone call

Phone call from their local site at week four after randomisation to confirm:

- Titration competency
- Adverse events

#### Week 8: Phone call

Phone call from their local site at week eight after randomisation to confirm:

- Titration competency
- Adverse events

# 3 month: Visit 2 (feasibility only)

- HbA1c
- Creatinine
- Medication count

- Adverse events
- Titration competency

# 6 month: Visit 3 (feasibility only)

- HbA1c
- Creatinine
- B12 levels, LFTs, total cholesterol, LDL and HDL cholesterol
- Medication count
- Adverse events
- Titration competency

# GP/participant questionnaire Mail Out (Issued after 4 months, annually and at end of study)

Participant questionnaire

- Self reported morbidity (CVD, cancer, T2DM)
- Medication adherence
- Health service use in past 12 months
- EuroQoL EQ-5D
- Treatment satisfaction/SF-8
- Self-Adverse events

GP questionnaire

- Vital status i.e. alive or dead
- Morbidity (CVD, cancer, T2DM)
- Current prescribed medication
- Adverse events
- Whether participant has become pregnant

Participants and GPs will be instructed to return the completed questionnaires to the DTU in freepost envelopes. If necessary, reminders will be sent after 4 and 8 weeks for the annual questionnaire. Participants will be contacted by phone if they do not respond to the reminders. Annual questionnaires will not be sent within 4 weeks of the end of study questionnaires being issued.

Participants and GPs will be reminded about the potential risks of taking metformin when they receive their four month questionnaire in the feasibility phase and the annual questionnaire in the full study.

When a participant or GP indicates that a primary or secondary endpoint has occurred following receipt of the annual questionnaire, information on this event will be collected immediately. We will also use information from the Office for National Statistics, the Cancer Registry and Health Episode Statistics to assess whether participants have experienced a study endpoint.

#### 11.3.2 Additional Information

•B12 levels, LFTs, total cholesterol, LDL and HDL cholesterol will be collected at baseline and 6 months. B12 and LFT results will be reviewed following the feasibility phase to inform a decision on whether it is necessary to include these measures in the full study.

•HbA1c and serum creatinine will be collected at baseline, 3 months, and 6 months. Baseline HbA1c and serum creatinine should be used for assessment of eligibility. Creatinine results will be reviewed following the feasibility phase to inform a decision whether it is necessary to centrally monitor renal function in the full study.

•Feedback about study participation, including how to optimise medication adherence, will be sought through the invitation of a subset of volunteers to participate in focus groups.

•We will use information received from the Office for National Statistics, the National Cancer Registry and Health Episode Statistics to assess clinical primary and secondary outcomes. Any events found will be added manually to the GLINT Trial Management System Database.

All participants in the feasibility phase of the study will continue into the full study and receive scheduled assessments as described in Appendix 1.

